# 12.1.1.3 Timing of Dose Administration

Trial treatment of pembrolizumab may be administered up to 3 days before or after the scheduled Day 1 of each pembrolizumab cycle due to administrative reasons

#### 12.1.2 Reduction Level 1 Treatment Schedule

If the starting treatment schedule described in Section 12.1.1 is not considered tolerable based on the incidence of dose-limiting toxicities (DLTs) (Section 20), the safety of the following treatment schedule ("Reduction Level 1") will be explored. If Reduction Level 1 is considered to be well-tolerated, in accordance with the rules of the "6 + 3" study design and the protocoldefined DLTs, the study will move into Part B (Simon Two-Stage) and will employ this treatment schedule. If  $\geq 3$  patients in 6 or 9 experience a DLT, then the investigational regimen will be considered too toxic and enrollment into the study will be discontinued.

#### 12.1.2.1 **Reduction Level 1 GX-188E**

The modification to GX-188E administration at Reduction Level 1 involves removal of the GX-188E vaccination at Week 2 Day 1. At Reduction Level 1, GX-188E will be administered Week 1 Day 1, Week 4 Day 1, Week 7 Day 1, Week 13 Day 1, Week 19 Day 1 and Week 46 Day 1(Optional).

#### 12.1.2.2 Reduction Level of Pembrolizumab

The dosage and frequency for pembrolizumab will not be modified. Patients will receive the regimen for pembrolizumab as described in Section 12.1.1.2

**Table 3. Investigational Treatment Schedules** 

Treatment Schedule	GX-188E	Pembrolizumab (P)
Starting Schedule	Week 1 Day 1, Week 2, Week 4, Week 7, Week 13, Week 19 and Week 46 (Optional)	200 mg Day 1 q 3 weeks
Reduction Level 1	Week 1 Day 1, Week 4, Week 7, Week 13, Week 19, and Week 46 (Optional) (remove Week 2)	200 mg Day 1 q 3 weeks (unchanged)

# 12.2 General Dosing Adjustments and Delays and Supportive Care Instructions

Treatment or visit delays for public holidays or weather conditions do not constitute a protocol violation.

# 12.2.1 Dose Modification and Toxicity Management for Immune-related AEs Associated with Pembrolizumab

AEs associated with pembrolizumab exposure may represent an immune-related response. These irAEs may occur shortly after the first dose or several months after the last dose of pembrolizumab treatment and may affect more than one body system simultaneously. Therefore, early recognition and initiation of treatment is critical to reduce complications. Based on existing clinical study data, most irAEs were reversible and could be managed with interruptions of pembrolizumab, administration of corticosteroids and/or other supportive care. For suspected irAEs, ensure adequate evaluation to confirm etiology or exclude other causes. Additional procedures or tests such as bronchoscopy, endoscopy, skin biopsy may be included as part of the evaluation. Dose modification and toxicity management guidelines for irAEs associated with pembrolizumab are provided in Table 4.

# Table 4. Dose Modification and Toxicity Management Guidelines for Immune-related AEs Associated with Pembrolizumab.

#### General instructions:

- 1. For Severe and life-threatening irAEs, should be treated with IV corticosteroid should be initiated first corticosteroids followed by oral steroidsteroids. Other immunosuppressive treatment should be initiated begin if the irAEs cannot beare not controlled by corticosteroids.
- 2. Pembrolizumab must be permanently discontinued if the irAE does not resolve or the corticosteroid dose is not ≤10 mg/day within 12 weeks of the last pembrolizumab treatment.
- 3. The corticosteroid taper should begin when the irAE is  $\leq$  Grade 1 and continue at least 4 weeks.
- 4. If pembrolizumab has been withheld, pembrolizumab may resume after the irAE decreased to ≤ Grade 1 after corticosteroid taper.

	Toxicity grade (CTCAE v4.0 or			
	the most recent	Action with	Corticosteroid and/or	
irAEs	version)	pembrolizumab	other therapies	Monitor and follow-up
Pneumonitis	Recurrent Grade 2, Grade 3 or 4	Permanently discontinue	
 
Administer         corticosteroids         (initial dose of 1-2         mg/kg prednisone         or equivalent)         followed by taper
 
Add prophylactic         antibiotics for         opportunistic         infections
 
	
 
Monitor participants for signs and symptoms of pneumonitis
 
Evaluate participants with suspected pneumonitis with radiographic imaging and initiate corticosteroid treatment
 

Diarrhea / Colitis	Grade 2 or 3	Withhold	Administer     corticosteroids     (initial dose of 1-2     mg/kg prednisone     or equivalent)     followed by taper	Monitor participants for signs and symptoms of enterocolitis (ie, diarrhea, abdominal pain, blood or mucus in stool with or without fever) and of bowel
	Recurrent Grade 3 or Grade 4	Permanently discontinue		perforation (ie, peritoneal signs and ileus).  Participants with ≥ Grade 2 diarrhea suspecting colitis should consider GI consultation and performing endoscopy to rule out colitis.  Participants with diarrhea/colitis should be advised to drink liberal quantities of clear fluids. If sufficient oral fluid intake is not feasible, fluid and electrolytes should be substituted via IV infusion.
AST or ALT elevation or Increased Bilirubin	Grade 2 ª	Withhold	Administer corticosteroids (initial dose of 0.5- 1 mg/kg	Monitor with liver function tests (consider weekly or more frequently until liver

	1		I 1:	
			prednisone or equivalent) followed by taper	enzyme value returned to baseline or is stable
	Grade 3 b or 4 c	Permanently discontinue	Administer     corticosteroids     (initial dose of 1-2     mg/kg prednisone     or equivalent)     followed by taper	
Type 1 diabetes mellitus (T1DM) or Hyperglycemia	New onset T1DM or Grade 3 or 4 hyperglycemia associated with evidence of β-cell failure	Withhold d	Initiate insulin replacement therapy for participants with T1DM     Administer antihyperglycemic in participants with hyperglycemia	Monitor participants for hyperglycemia or other signs and symptoms of diabetes.
Hypophysitis	Grade 2 Grade 3 or 4	Withhold or permanently discontinue d	Administer     corticosteroids     and initiate     hormonal     replacements as     clinically	Monitor for signs and symptoms of hypophysitis (including hypopituitarism and adrenal insufficiency)
Hyperthyroidism	Grade 2	Continue	
 
indicated.
 
Treat with non-selective betablockers (eg, propranolol) or thionamides as appropriate
 
	
 
Monitor for signs and symptoms of thyroid disorders.
 

	Grade 3 or 4	Withhold or permanently discontinue d		
Hypothyroidism	Grade 2, 3, 4	Continue	Initiate thyroid replacement hormones (eg, levothyroxine or liothyroinine) per standard of care	Monitor for signs and symptoms of thyroid disorders.
Nephritis: grading according to increased creatinine or acute kidney injury	Grade 2 Grade 3 or 4	Withhold  Permanently discontinue	Administer     corticosteroids     (prednisone 1-2     mg/kg or     equivalent)	Monitor changes of renal function
Myocarditis	Grade 1	Withhold	Based on severity of AE administer corticosteroids	Ensure adequate evaluation to confirm etiology and/or exclude other causes
	Grade 2, 3 or 4	Permanently discontinue		
All Other immune- related AEs	Persistent Grade 2 Grade 3	Withhold or discontinue based on the	Based on severity of AE administer corticosteroids	Ensure adequate evaluation to confirm etiology or exclude other causes
	Grade 4 or recurrent Grade 3	type of event e Permanently discontinue		

- a. AST/ALT: >3.0 5.0 x ULN if baseline normal; >3.0 5.0 x baseline, if baseline abnormal; bilirubin:>1.5 3.0 x ULN if baseline normal; >1.5 3.0 x baseline if baseline abnormal
- b. AST/ALT: >5.0 to 20.0 x ULN, if baseline normal; >5.0 20.0 x baseline, if baseline abnormal; bilirubin:>3.0 10.0 x ULN if baseline normal; >3.0 10.0 x baseline if baseline abnormal
- c. AST/ALT: >20.0 x ULN, if baseline normal; >20.0 x baseline, if baseline abnormal; bilirubin: >10.0 x ULN if baseline normal; >10.0 x baseline if baseline abnormal
- d. The decision to withhold or permanently discontinue pembrolizumab is at the discretion of the investigator or treating physician. If control achieved or ≤ Grade 2, pembrolizumab may be resumed.
- e. Events that require discontinuation include but are not limited to: Guillain-Barre Syndrome, encephalitis, Stevens-Johnson Syndrome and toxic epidermal necrolysis.

Requirements for treatment discontinuation are not strict and individual situations will be evaluated on a case-by-case basis. Treatment discontinuation for both non-hematological and hematological toxicities will be based on the Principal Investigator's judgment following discussion with the Sponsor's Medical Monitor.

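### The case-by-case discontinuation paragraph below Table 4 makes no exception for the permanent stops ordered in Table 4, Table 5 and Section 19.1

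*Protocol*

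**What the plan says.** The paragraph that closes Protocol Section 12.2.1, below the Table 4 footnotes, has two sentences. The first is "Requirements for treatment discontinuation are not strict and individual situations will be evaluated on a case-by-case basis". The second begins "Treatment discontinuation for both non-hematological and hematological toxicities will be based on the Principal" and goes on to name the Investigator's judgment, exercised after discussion with the Sponsor's Medical Monitor. It states no exception and refers to no other section.

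Four other places in the protocol set fixed stops:

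- **Table 4, rows.** The action for several grades of immune-related event is "Permanently discontinue", with no discretion footnote attached.
- **Table 4, general instruction 2.** "Pembrolizumab must be permanently discontinued if the irAE does not resolve or the corticosteroid dose is not" at or below 10 mg/day within 12 weeks of the last pembrolizumab dose.
- **Table 4, footnote e.** "Events that require discontinuation include but are not limited to" four named conditions: Guillain-Barre syndrome, encephalitis, Stevens-Johnson syndrome and toxic epidermal necrolysis.
- **Table 5 and Section 19.1.** Table 5 permanently stops study drug for Grade 3 or 4 infusion reactions, and for Grade 2 reactions that occur despite adequate premedication. Section 19.1 places recurrent Grade 2 pneumonitis in a list of reasons for which treatment must stop.

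Table 4 also grants discretion, but locally. Footnote d says "The decision to withhold or permanently discontinue pembrolizumab is at the discretion of the investigator or treating physician" and is attached to type 1 diabetes/hyperglycemia, hypophysitis and hyperthyroidism. The row for other immune-related events at persistent Grade 2 or at Grade 3 reads "Withhold or discontinue based on the" type of event.

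**The concern.** Table 4 separates events for which pembrolizumab must end from events for which the physician may choose. A paragraph in the same section that calls the requirements not strict, and hands all toxicity stops to judgment, removes that separation when followed as written. The events concerned include myocarditis, pneumonitis and severe hepatic toxicity, where a fixed stop protects the patient.

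The practical stake is the instruction to sites and the classification of what they do. SAP Section 9 lists protocol deviations and summarizes them by type. If a further dose is given after an event with an ordered stop, a site can cite the closing paragraph and a monitor can cite the table row. At least eight sites are planned (Protocol Section 10.6), so readings may differ between them.

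**Working it through.** No arithmetic beyond counting applies. The check is to classify every Table 4 category, add the stops outside its rows without double-counting, and look for a rule of precedence.

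**Step 1. Table 4 categories.**

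| Category | Fixed permanent stop | Local choice |
|---|---|---|
| Pneumonitis | Recurrent Grade 2, Grade 3 or 4 | none |
| Diarrhea/colitis | Recurrent Grade 3, Grade 4 | none |
| AST/ALT/bilirubin | Grade 3 or 4 | none |
| Nephritis | Grade 3 or 4 | none |
| Myocarditis | Grade 2, 3 or 4 | none |
| All other immune-related | Grade 4, recurrent Grade 3 | persistent Grade 2, Grade 3 |
| Type 1 diabetes/hyperglycemia | none | footnote d |
| Hypophysitis | none | footnote d |
| Hyperthyroidism | none | footnote d |
| Hypothyroidism | none | none (continue only) |

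- Categories with an unqualified permanent stop: 6. With footnote d: 3. Continue only: 1. Check: 6 + 3 + 1 = 10.
- Of the 6, 5 have no row offering a choice and 1 (all other) is mixed.
- Categories with local discretion: 3 + 1 = 4.

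**Step 2. Fixed stops beyond the rows.**

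- General instruction 2 is additional. It applies across immune-related events and rests on resolution and steroid dose, not grade.
- Footnote e is not additional. Its marker sits in the discretionary cell of the all-other row, so it narrows a category already counted.
- The Section 19.1 item repeats part of the Table 4 pneumonitis row. It matters because it puts the stop under a mandatory heading outside the table.
- Table 5 adds two stops that appear in neither Table 4 nor Section 19.1: Grade 3/4 infusion reactions, and Grade 2 reactions despite adequate premedication.

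**Step 3. Is there a rule that settles the conflict?** The closing paragraph has no carve-out. Neither the protocol nor the SAP contains a precedence clause. The provisions that bear on continued dosing are these:

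- The closing paragraph itself requires Medical Monitor discussion.
- Section 10.8 requires that treatment be well tolerated and that the investigator and sponsor agree the patient may be benefitting.
- Section 12.2.4 asks that immune-related events of Grade 2 or higher be discussed immediately with the sponsor.
- The Safety Monitoring Committee meets at least quarterly in Parts B and C.
- General instruction 4 says "If pembrolizumab has been withheld, pembrolizumab may resume after the irAE decreased to" Grade 1 or lower after a steroid taper. This concerns resumption after withholding, not after an event with an ordered permanent stop.

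All of these provide consultation, review or conditions for going on. None says that a fixed stop stays fixed.

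**Step 4. Worked case.** A patient has Grade 3 myocarditis. The Table 4 row orders a permanent stop of pembrolizumab and has no footnote d. The closing paragraph bases the same decision on judgment after discussion with the Medical Monitor. Both instructions are in Section 12.2.1, and they give different answers if the judgment is to continue.

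**The case against.** The best reply is that the texts can be read together. Table 4's action column, its general instruction 2 and footnote d all speak of pembrolizumab. The closing paragraph speaks of treatment discontinuation and includes hematological toxicities, for which Table 4 has no row. Table 4 sets no stop for GX-188E either. The paragraph may therefore be a residual rule for GX-188E and for toxicities outside the tables, with the specific rows prevailing over the general sentence. Tables 4 and 5 are also titled as guidelines. Section 19.1 is not strict throughout, since its mandatory list includes a complete-response item that is optional. Footnote e is an open list, so it too needs judgment.

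Much of this is fair, and the residual reading is plausible. But the paragraph states no such limit, and the protocol does not say that specific text prevails. Its first sentence describes the discontinuation requirements themselves, in the same section as the table that sets them. The operative wording of instruction 2 and footnote e is mandatory despite the table's title. The distinction between pembrolizumab and the whole regimen does not reconcile Table 5 or Section 19.1, which refer to study drug or study treatment. And if discretion applied everywhere, footnote d would have little purpose; it also names a different decision-maker.

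A reader might go further and infer that the paragraph tells sites to keep dosing. It does not. Nor is it right that nobody could classify a further dose: dosing against a permanent-stop row departs from an explicit instruction, and dosing without the Medical Monitor discussion breaches the closing paragraph itself. Classification is disputable, not impossible.

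**Conclusion.** The paragraph is wrong as written and should be corrected. Followed literally, it loosens permanent stops in 6 of 10 Table 4 categories, in general instruction 2, for the events named in footnote e within the all-other row, in Table 5, and for the pneumonitis item in Section 19.1. The conclusion rests on the wording alone and on the absence of a carve-out or precedence clause in either document; confidence in that is high. Existing consultation requirements reduce the risk, so this is a point to fix and not a ground for stopping the trial.

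Two further inferences are unsupported. The documents give no incidence for the events concerned, so the number of patients affected cannot be estimated. Nothing in them shows that the conflict would change the 24-week response rate, and no such effect is claimed.

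**What to change.** Replace the closing paragraph of Section 12.2.1 with:

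> *Case-by-case judgment by the Principal Investigator, after discussion with the Sponsor's Medical Monitor, applies only to toxicities for which Table 4 (including its general instructions and footnote e), Table 5 or Section 19.1 does not order permanent discontinuation.*

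Table 5 has to be named. A sentence citing only Table 4 and Section 19.1 would place Grade 3/4 infusion reactions, including anaphylaxis, inside the discretionary group.

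In Section 19.1, where recurrent Grade 2 pneumonitis is the only toxicity listed under the mandatory heading, add a cross-reference to the permanent stops in Tables 4 and 5.

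The local discretion in footnote d and in the all-other row is kept. The cost is one sentence and one cross-reference in the next amendment, a memo to sites, and slightly less flexibility for investigators. No procedures, visits or patients are added.

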# Dose modification and toxicity management of infusion-reactions related to pembrolizumab

Pembrolizumab may cause severe or life threatening infusion-reactions including severe hypersensitivity or anaphylaxis. Signs and symptoms usually develop during or shortly after drug infusion and generally resolve completely within 24 hours of completion of infusion. Dose modification and toxicity management guidelines on pembrolizumab associated infusion reaction are provided in Table 5.

Table 5. Pembrolizumab Infusion Reaction Dose modification and Treatment Guidelines

NCI CTCAE Grade	Treatment	Premedication at Subsequent Dosing
Grade 1 Mild reaction; infusion interruption not indicated; intervention not indicated	Increase monitoring of vital signs as medically indicated until the participant is deemed medically stable in the opinion of the investigator.	None
Grade 2 Requires therapy or infusion interruption but responds promptly to symptomatic treatment (e.g., antihistamines, NSAIDs, narcotics, IV fluids); prophylactic medications indicated for ≤24 hrs.	
 
Stop Infusion.
 
Additional appropriate medical therapy may include but is not limited to:
 
IV fluids
 
Antihistamines
 
NSAIDs
 
Acetaminophen
 
Narcotics
 
Increase monitoring of vital signs as medically indicated until the participant is deemed medically stable in the opinion of the investigator.
 
If symptoms resolve within 1 hour of stopping drug infusion, the infusion may be restarted at 50% of the original infusion rate (e.g. from 100 mL/hr. to 50 mL/hr.). Otherwise dosing will be held until symptoms resolve and the participant should be premedicated for the next scheduled dose.
 
Participants who develop Grade 2 toxicity despite adequate premedication should be permanently discontinued from further study drug treatment
 
	Participant may be premedicated 1.5h (± 30 minutes) prior to infusion of study interventionwith:  Diphenhydramine 50 mg po (or equivalent dose of antihistamine).  Acetaminophen 500-1000 mg po (or equivalent dose of analgesic).
Grade 3: Prolonged (i.e., not rapidly responsive to symptomatic medication and/or brief interruption of infusion); recurrence of symptoms following initial improvement; hospitalization indicated for other clinical sequelae (e.g., renal impairment, pulmonary infiltrates) Grade 4: Life-threatening; pressor or ventilator support indicated	Stop Infusion.     Additional appropriate medical therapy may include but is not limited to:     Epinephrine**     IV fluids     Antihistamines     NSAIDs     Acetaminophen     Narcotics     Oxygen     Pressors     Corticosteroids     Increase monitoring of vital signs as medically indicated until the participant is deemed medically stable in the opinion of the investigator.     Hospitalization may be indicated.  **In cases of anaphylaxis, epinephrine should be used immediately. Participant is permanently discontinued from further study drug treatment.	No subsequent dosing

Appropriate resuscitation equipment should be available at the bedside and a physician readily available during the period of drug administration. For further information, please refer to the Common Terminology Criteria for Adverse Events v4.0 or the most recent version (CTCAE) at http://ctep.cancer.gov

# 12.2.3 Other Allowed Dose Interruption for Pembrolizumab

Pembrolizumab may be interrupted for situations other than treatment-related AEs such as medical or surgical events and/or unforeseen circumstances not related to study intervention. However, study intervention is to be restarted within 3 weeks or 21 days of the originally scheduled dose and within 42 days of the previously administered dose, unless otherwise discussed with the Sponsor. The reason for interruption is to be documented in the patient's study record.

# 12.2.4 Supportive Care Guidelines for Events of Clinical Interest and Immunerelated Adverse Events (irAEs)

Events of clinical interest of a potential immunologic etiology (irECIs) may be defined as an adverse event of unknown etiology, associated with drug exposure and is consistent with an immune phenomenon. irAEs may be predicted based on the nature of the pembrolizumab compound, its mechanism of action, and reported experience with immunotherapies that have a similar mechanism of action. Special attention should be paid to AEs that may be suggestive of potential irAEs. An irAE can occur shortly after the first dose or several months after the last dose of treatment.

If an irAE is suspected, efforts should be made to rule out neoplastic, infectious, metabolic, toxin or other etiologic causes prior to labeling an adverse event as an irAE. Patients who develop a Grade 2 or higher irAE should be discussed immediately with the Sponsor.

#### 13.0 **Prior Treatment**

Patients should have disease that is relapsed or refractory to standard-of-care treatment regimens. Patients should not be candidates for other approved, standard-of-care therapies. Patients with newly-diagnosed disease that is not amenable to definitive surgery and who refuse treatment with standard regimens are permitted with clear Investigator documentation. In addition, the determination that there are "no available therapies that will confer clinical benefit" for the patient will be based on the medical opinion of the Principal Investigator.

Reasonable efforts will be made to determine all relevant prior treatments received by the patient during the Screening period. All previous cancer treatments, including systemic

therapies, radiation and/or surgical procedures, should be recorded on the patients' case report forms (CRF).

# 14.0 Meals and Dietary Restrictions

Participants should maintain a normal diet unless modifications are required to manage an AE such as diarrhea, nausea, or vomiting.

#### 15.0 Concomitant Treatments

All treatments that the investigator considers necessary for a patient's welfare may be administered at the discretion of the Investigator in keeping with the community standards of medical care. All concomitant medications must be recorded on the CRF, including all prescription, over-the-counter (OTC), herbal and vitamin supplements, and IV medications and fluids. The reason for treatment, name of the drug, dosage, route, and start and stop dates of administration for each concomitant medication will also be reported on the CRF. All changes (e.g., changes in dose, discontinuation, etc.) in concomitant treatments that occur during the trial period should also be reported.

All concomitant medications received to the subject within 28 days prior to the first dose through the end of the subject's study participation should be recorded. (However, during the follow-up period after the end of the clinical trial, only the data about the antineoplastic therapy (surgical therapy, chemotherapy, radiation therapy, etc.) treated after the end of the subject's study participation is recorded.). Concomitant medications administered 30 days after the last dose of study treatment should be recorded for SAEs and events of clinical interest (ECIs) as defined in Section 20.8

